The data for analysis will be captured by these patient completed forms to provide demographic information, including sex, age, and race/ethnicity. We will measure height and weight prior to CAP/FibroScan testing.

Metabolic Syndrome:

Subjects will use a form to check YES or NO for comorbid components of the metabolic syndrome that they may or may not have:

- Obesity/overweight
- Diabetes mellitus
- Hypertension
- Hypercholesterolemia
- Hypertriglyceridemia
- Gout or elevated uric acid

Other Health Conditions:

Subjects will use a form to check YES or NO for other health conditions they may or may not have:

- Heart disease
- Heart attack
- Arrhythmia
- Stroke
- Arthritis
- Osteopenia/osteoporosis
- Hypothyroidism
- Low Vitamin D
- Low testosterone
- Menopausal state
- Inflammatory bowel disease (ulcerative colitis or Crohn's disease)
- Cancer
 - Skin: melanoma
 - Skin: basal cell or squamous cell cancers

- Other type of cancers: lymphoma; leukemia; head or neck; thyroid; brain; breast; lung; stomach; colon; liver; ovary; uterus; prostate; bone

Diet:

Subjects will fill out a form using a 5-point scale of the frequency of their average weekly dietary intake of specific food types: (A. 0 days, B. 1-2 days, C. 3-4 days, D. 5-6 days, E. 7 days per week)

- Proteins: eggs, cheese, beans, fish, chicken, turkey, beef, pork
- Starchy carbohydrates: breads, rolls, pasta, cereals, potatoes, rice, corn, peas, lima beans
- Non-starchy vegetables: lettuces, kale, carrots, green beans, broccoli, peppers, onions, cucumber
- Fats: butter, margarine, avocado, oils (olive, safflower, cottonseed, peanut, sesame, walnut)
- Nuts: peanuts, walnuts, cashews, almonds, macadamias, peanuts
- Sugars or Syrups: sugar, high fructose corn syrup (sodas), maple or corn syrups
- Fast food meals
- Eating out at restaurants

Exercise:

Subjects will fill out a form using a 5-point scale of the frequency of their average weekly exercise:

- (A. 0 days, B. 1-2 days, C. 3-4 days, D. 5-6 days, E. 7 days per week)
- Cardiovascular: brisk walking, jogging, biking, treadmill, stationary bike, stair stepper, elliptical, swimming laps
 - Strength: weight lifting, resistance machines or cords

Alcohol:

Subjects will fill out a form quantifying their average weekly total of alcoholic drinks:

(1 drink= 12 oz. beer, 6 oz. wine, 1.5 oz. hard liquor; 3 oz. brandy, sherry, liqueur):

- None
- 1-2 drinks/week
- 3-4 drinks/week
- 5-6 drinks/week
- 7-8 drinks/week
- 9-10 drinks/week

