- 10-12 drinks/week
- 13-14 drinks/week
- 14-20 drinks/week
- 21 or more drinks/week

Other Liver Diseases:

Subjects will check YES or NO for other liver-related diseases that they may or may not have:

- Hepatitis B alone
- Hepatitis B with Hepatitis D
- Hepatitis C
- Hepatitis E
- Autoimmune hepatitis
- Primary biliary cholangitis
- Primary sclerosing cholangitis
- Iron overload
- Alpha-1-antitrypsin deficiency

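### The alcohol item has overlapping answer boxes at 10 and at 14 drinks a week, with no rule for choosing between them; the effect is probably small, and the fix is a form edit.

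*Combined protocol and SAP*

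**What the plan says.** The alcohol item appears twice, under Alcohol in the protocol's Data Collection section and under Alcohol in the SAP's Data Collection section. The answer list and drink definition are the same in both.

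- The upper part of the list runs "9-10 drinks/week", "10-12 drinks/week", "13-14 drinks/week", "14-20 drinks/week", "21 or more drinks/week".
- The drink definition is "1 drink= 12 oz. beer, 6 oz. wine, 1.5 oz. hard liquor; 3 oz. brandy, sherry, liqueur".
- On the use of the item, the SAP states under Demographics: "The data for analysis will be captured by these patient completed forms".

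The SAP's Data Analysis section sets a secondary goal of finding factors associated with fat, with or without stiffness. It compares categorical variables by contingency table and carries factors with univariate p ≤ 0.05 into a multivariate analysis. It does not name alcohol as one of those factors. No section says how an answer of exactly 10 or 14 is to be coded, and none gives the alcohol strength of any beverage.

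**The concern.** Answer boxes for a single-choice question should not share values. Here two values are shared, and both are plausible answers: 14 is two drinks a day, and 10 is a round number. Two people with the same intake can end up in different categories, depending only on which box each happens to tick.

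This matters because the form is the only alcohol information the study collects. The eligibility lists set no alcohol limit, so the item is all an analyst would have for asking whether intake goes with fat or stiffness. The SAP also rules out individual follow-up, so an ambiguous answer cannot readily be queried afterwards.

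The drink definition raises a separate, weaker question: one drink is 1.5 oz of hard liquor but 3 oz of brandy, sherry or liqueur.

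**Working it through.** The plan gives no figure to reproduce on this point.

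**1. Do the boxes overlap?** The ten boxes, taken from the form, are 0; 1-2; 3-4; 5-6; 7-8; 9-10; 10-12; 13-14; 14-20; 21 or more. For each whole number from 0 to 29, count the boxes that contain it.

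- 10 falls in two boxes (9-10 and 10-12).
- 14 falls in two boxes (13-14 and 14-20).
- The other 28 values fall in exactly one box, and there are no gaps.

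The lower boxes are all mutually exclusive, so the overlaps look like slips. They appear in both parts of the document, so they are not a text-extraction fault.

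**2. Which splits are lost?**

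- 14 or fewer against 15 or more cannot be made, because one box mixes 14 with 15-20.
- 10 or fewer against 11 or more cannot be made, because one box mixes 10 with 11-12.
- Splits at 8/9, 12/13 and 20/21 remain clean.

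**3. How many people have no unique box?** The inputs are N = 400 (the minimum, from Intended Use of the Data in the protocol), the share q who drink 9 to 20 a week (assumed 10%, range 5% to 20%), and an even spread over the 12 whole numbers 9 to 20 (assumed).

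Number ambiguous = N × q × 2/12.

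- q = 10%: 400 × 0.10 × 2/12 = 6.7, about 7 people, or 6.7/400 = 1.7% of the sample.
- q = 5%: 400 × 0.05 × 2/12 = 3.3.
- q = 20%: 400 × 0.20 × 2/12 = 13.3.
- At the maximum of 1,000 with q = 10%: 1,000 × 0.10 × 2/12 = 16.7.

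If answers heap on 10 or 14 the count would be higher. The documents give no distribution from which to judge that.

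**4. Side point: drink size.** Alcohol per form drink = volume × strength. All strengths are assumptions.

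| Beverage | Volume | Assumed strength | Alcohol per drink |
|---|---|---|---|
| Hard liquor | 1.5 oz | 35-45% | 0.53-0.68 oz |
| Brandy | 3 oz | 35-45% | 1.05-1.35 oz |
| Sherry | 3 oz | 15-20% | 0.45-0.60 oz |
| Liqueur | 3 oz | 15-40% | 0.45-1.20 oz |

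The two serving sizes match only if the 3 oz beverage has 1.5/3 = half the strength of hard liquor. Under the assumed range, a brandy drink holds between 1.05/0.675 = 1.6 and 1.35/0.525 = 2.6 times the alcohol of a liquor drink, and exactly twice at equal strength. Sherry is roughly consistent; liqueur depends on its strength.

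**The case against.** The strongest case on the other side is that this is an editorial slip with almost no consequence. Most of that stands.

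- No alcohol threshold enters eligibility, the disease staging or the primary proportions, so the main result is the same either way.
- Each overlap is a single whole number, so it can move a person by one adjacent box at most. The 14-20 box is wide, but it would still be wide as 15-20.
- No split at 10 or 14 is planned, and the SAP specifies contingency tables without a trend test.
- The people counted above have an ambiguous box; that does not make them wrongly classified.
- The technician rechecks the intake form before the scan and might catch a double tick, though without a rule the choice stays arbitrary.

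A reader might infer that intake is shown to be misclassified in the secondary analysis. The documents do not support that: alcohol is a candidate factor only by inference from its presence on the forms, and the number affected rests on assumptions.

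A reader might also take the brandy serving as an internal contradiction. It is not one. The volumes conflict only if brandy is more than half as strong as hard liquor, and the documents give no strengths. Nor do they say how many participants drink brandy, so no study-level size can be attached.

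What the objection does not remove is the overlap itself. It sits in the instrument that supplies the analysis data, has no tie-break rule, and costs nothing to correct.

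**Conclusion.** The overlap at 10 and 14 is proven from the document alone. Its practical effect is probably small: about 7 of 400 people without a unique category, or 3 to 13, given the assumed share of drinkers and the assumed even spread. It bears on any use of alcohol in the secondary analysis of associated factors and on any later wish to divide the data at 10 or 14. It does not bear on the primary proportions.

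The brandy serving is a side point only. It holds if brandy and hard liquor are of similar strength, which is an assumption from outside the documents, and it is a reason to check the definition.

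**What to change.** - Change the upper boxes to 9-10, 11-12, 13-14, 15-20, and 21 or more, in both the protocol and the SAP. Every whole number then has one box, and splits at 10/11 and 14/15 become possible. Before the first participant this is a form edit with no added burden.
- If forms are already in use, merge 9-10 with 10-12 and 13-14 with 14-20 for analysis, giving 9-12 and 13-20. This removes the ambiguity at a small loss of detail, but it does not recover a split at 10 or 14.
- Have the sponsor check the serving definition. If brandy and full-strength liqueurs are confirmed to be of similar strength to hard liquor, list them with it at 1.5 oz and keep 3 oz for sherry and similar drinks. Merging boxes cannot correct this on completed forms, so the check is best made before the form is used.
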